### **14.2 Compliance**

This study will be conducted in compliance with the protocol, GCP, and all applicable regulations, including the Federal Food, Drug and Cosmetic Act, U.S. applicable Code of Federal Regulations (title 21), and any IEC requirements relative to clinical studies. The study will also be conducted in compliance with the recommendations laid down in the most recent version of the Declaration of Helsinki, with the exception that registration of such Phase 1 trials in a publicly accessible database is not mandatory.

### **14.3 Liability**

If a bodily injury is sustained, resulting directly from the use of the study drug, the Sponsor will reimburse for reasonable physician fees and medical expenses necessary for diagnosis and treatment of only the bodily injury, provided that the injury is not due to a negligent or wrongful act or omission by the study doctor and his/her staff, in which case the clinical site would cover associated fees.

### **14.4 Quality Assurance Program**

The clinical sites have established Quality Control (QC) and Quality Assurance (QA) systems with written SOPs to ensure that the study will be conducted and data will be generated, recorded, and reported in compliance with the protocol, GCP, and applicable regulatory requirements. A rigorous QC program is applied to ensure accuracy of all data and reports.

### **14.5 Audits, Inspections and Monitoring**

In accordance with the principles of GCP and GLP, the study may be inspected by the QA unit of the clinical sites, regulatory authorities, and the Sponsor. The Sponsor is entitled to access information about the status of the study and to review the original documents of the study.

## **15. Confidentiality and Retention of Essential Documentation**

This document contains trade secrets and commercial information that is confidential and may not be disclosed to third parties. Persons to whom this study protocol is disclosed must be informed that all the information herein is confidential and may not be further divulged. These restrictions will apply as well to all future communications if deemed privileged or confidential. Publication of the study results may only be allowed with written permission from the Sponsor.

Study documents should be retained for a minimum of 2 years after the last approval of a marketing application in an International Conference on Harmonization (ICH) region and until there are no pending or contemplated marketing applications in an ICH region or until at least 2 years have elapsed since the formal discontinuation of clinical development of the study intervention. These documents should be retained for a longer period, however, if required by local regulations. No records will be destroyed without the written consent of the sponsor, if applicable. It is the responsibility of the sponsor to inform the investigator when these documents no longer need to be retained.

**Table 5. Site Reactions to Injections and Infusions DAIDS Grading Table**

PARAMETER	GRADE 1 MILD	GRADE 2 MODERATE	GRADE 3 SEVERE	GRADE 4 POTENTIALLY LIFE-THREATENING
Injection Site Pain or Tenderness Report only 1	Pain or tenderness causing no or minimal limitation of use of limb	Pain or tenderness causing greater than minimal limitation of use of limb	Pain or tenderness causing inability to perform usual social and functional activities	Pain or tenderness causing inability to perform basic self-care function OR hospitalization indicated
Injection Site Erythema or Redness* Report only 1 (> 15 years of age)	2.5 to <5 cm in diameter OR 6.25 to <25 cm  surface area AND symptoms causing no or minimal interference with usual social and functional activities	≥5 to <10 cm in diameter OR ≥25 to <100 cm  surface area OR Symptoms causing greater than minimal interference with usual social and functional activities	≥10 cm in diameter OR ≥100 cm  surface area OR ulceration OR secondary infection OR phlebitis OR sterile abscess OR drainage OR symptoms causing inability to perform usual social and functional activities	Potentially life-threatening consequences (eg, abscess, exfoliative dermatitis, necrosis involving dermis or deeper tissue)
Injection Site Induration or Swelling Report only 1 (> 15 years of age)	2.5 to <5 cm in diameter OR 6.25 to <25 cm  surface area AND symptoms causing no or minimal interference with usual social and functional activities	≥5 to <10 cm in diameter OR ≥25 to <100 cm  surface area OR Symptoms causing greater than minimal interference with usual social and functional activities	≥10 cm in diameter OR ≥100 cm  surface area OR ulceration OR secondary infection OR phlebitis OR sterile abscess OR drainage OR symptoms causing inability to perform usual social and functional activities	Potentially life-threatening consequences (eg, abscess, exfoliative dermatitis, necrosis involving dermis or deeper tissue)
Injection Site Pruritus	Itching localized to the injection site that is relieved spontaneously or in <48 hours of treatment	Itching beyond the injection site that is not generalized OR itching localized to the injection site requiring ≥48 hours treatment	Generalized itching causing inability to perform usual social and functional activities	NA

\* Injection Site Erythema or Redness should be evaluated and graded using the greatest single diameter or measured surface area.

Ae _{interval}	Amount of drug excreted in urine for each time interval, calculated as the urine concentration multiplied by the urine volume Cumulative urinary excretion from time zero to time t, calculated as the sum of the amounts excreted over each collection interval.		
AUC	Area under the curve		
AUC ₀₋₂₄	Area under the concentration-time curve from time zero to 24 hours post-dose		
AUC ₀₋₇₂	Area under the concentration-time curve from time zero to 72 hours post-dose		
AUC _{0-t}	Area under the concentration-time curve from time zero to the last non-zero concentration		
AUC _{0-inf}	Area under the concentration-time curve from time zero to infinity (extrapolated)		
BLQ	Below lower limit of quantification		
BMI	Body mass index		
BSA	Body Surface Area		
CI	Confidence interval		
CL/F	Apparent Body Clearance		
CLR	Renal clearance, calculated as Ae ₀₋₂₄ /AUC ₀₋₂₄		
Cmax	Maximum observed concentration		
СРК	Creatine phosphokinase		
CR/STBA Form	Confinement Report and Subjects To Be Analyzed Form		
CSR	Clinical study report		
CV	Coefficient of variation		
D_{sc}	Dose administered by Subcutaneous		
ECG	Electrocardio gram		
eGFR	estimated glomerular filtration rate		
ES	Estradiol		

Eloxx Pharmaceuticals

FDA	Food and Drug Administration		
Fe _{0-t}	Fraction (% dose) excreted unchanged		
GLM	Generalized linear model		
HBsAg	Hepatitis B		
HCV	Hepatitis C		
HEENT	Head, eyes, ears, nose, and throat		
HIV	Human Immunodeficiency Virus		
HR	Heart rate		
INR	International normalized ratio		
IV	Intravenous		
kg	Kilogram		
Kel	Elimination rate constant		
Kel Lower	The timepoint where K _{el} calculation begins.		
K _{el Upper}	The actual sampling time of the last measurable concentration used to estimate the $K_{\rm el}$.		
L	Liters		
Max	Maximum		
MedDRA	Medical Dictionary for Regulatory Activities		
MDRD	Modification of Diet in Renal Disease		
mg	Milligram		
Min	Minimum		
mL	Milliliter		
mmHg	Millimeters Mercury		
MSE	Mean Square Error		
PK	Pharmacokinetic		
PR	PR interval		
aPTT	Activated partial thromboplastin time		
PT	Preferred term (for adverse events); Prothrombin time (for coagulation tests)		
QT	QT interval		
QTcF	Fridericia's corrected QT interval		
RI	Renal Impairment		

Eloxx Pharmaceuticals

R _{max}	Maximum rate of urinary excretion, calculated by dividing the amount of drug excreted in each collection interval by the time over which it was collected		
SAE	Serious adverse event		
SAP	Statistical Analysis Plan		
SAS	Statistical Analysis System		
SC	Subcutaneous		
SD	Standard deviation		
SOC	System Organ Class		
SOPs	Standard operation procedures		
TEAEs	Treatment-emergent adverse events		
T _{½ el}	Elimination half-life		
T _{max}	Time of observed C _{max}		
T _{Rmax}	Time of maximal urinary excretion, calculated as the midpoint of the collection interval during which R _{max} occurred		
ULN	Upper limit of normal		
V _d /F	Apparent Volume of Distribution		
WHO DD	World Health Organization Drug Dictionary		

Eloxx Pharmaceuticals

1. Introduction

This statistical analysis plan (SAP) is intended to give a detailed description of the summaries and the analyses that will be generated for the present study by inVentiv or another statistical provider. Analyses specified in this plan are based on Eloxx Pharmaceuticals Study Protocol no. EL-008, Version Final 2.0, dated 06 Nov, 2018 (inVentiv Project No. 182023). Safety, tolerability, and pharmacokinetic (PK) analyses will all be described.

No change will be made without prior approval of the study Sponsor. No revision to the SAP is required for changes that do not affect the statistical analysis methods, definitions, or rules defined in this document. If changes made after the SAP has been finalized due to unforeseen circumstances and/or additional analyses are required to supplement the planned analyses described in the SAP, the changes and justification for the changes will be outlined in the clinical study report (CSR).

When applicable, all methodology and related processes will be conducted according to inVentiv's or another statistical provider's Standard Operating Procedures (SOPs) as appropriate.

Shells for all statistical tables, figures and listings referred to in this SAP will be displayed in a separate document.

2. Study Objective

2.1 Primary Objective

To determine the effect of various severities of renal impairment (RI) on the pharmacokinetics (PK) of ELX-02 following a single subcutaneous (SC) dose in subjects with normal renal function, mild, moderate, or severe renal impairment.

2.2 Secondary Objective

To assess the safety and tolerability of a single SC dose of ELX-02 in subjects with normal renal function, mild, moderate, or severe renal impairment.

3. Study Design

3.1 General Design

The study is a two-center, Phase 1, open-label, single dose, one-period, four-parallel-group, PK study in subjects with various severities of renal dysfunction and healthy volunteers. The study is intended for filing under the US Food and Drug Administration (FDA) regulations.

A total of approximately 24 to 26 healthy adult male or female volunteers will be enrolled.

Subjects will be enrolled into the trial and assigned to one of the 4 study groups. Six (6) subjects completing the study are targeted for each group of RI subjects (Groups 1 to 3) and 6 to 8 subjects will be included in the control group (Group 4). Attempts will be made to enroll at least two subjects of each gender in each group and subjects with various BMIs.

Subjects will be assigned to one of the following groups:

- Group 1 (Mild): 6 subjects with mildly decreased renal function: eGFR 60 89 mL/min/1.73 m²;
- Group 2 (Moderate): 6 subjects with moderately decreased renal function: eGFR 30 59 mL/min/1.73 m²;
- Group 3 (Severe): 6 subjects with severely decreased renal function: eGFR < 30 mL/min/1.73 m² and not requiring dialysis.
- Group 4 (Control): 6-8 healthy subjects with normal renal function: eGFR $\geq 90 \text{ mL/min}/1.73 \text{ m}^2$;

Group 1 (Mild) and Group 2 (Moderate) will be dosed first, in parallel, with an interim analysis performed (refer to Section 7).

Subjects with normal renal function (Group 4) will be matched with renally impaired (RI) subjects by age (\pm 10 years), gender, and BMI (\pm 15%). A mean matching procedure will be performed. Therefore 6 subjects completing the study are targeted for each of the RI groups (Groups 1 to 3) and 6 to 8 subjects will be included in the control group (Group 4).

3.2 Study Procedures

The overall schedule of procedures and assessments is provided in the protocol.

3.3 Drug Administration

Each subject will be administered a single SC dose of 1 mg/kg ELX-02 (Eloxx Pharmaceuticals, USA) on Day 1. The body weight of each subject will be measured on Day -1 (check-in) and this value will be used to calculate the exact individual dose of ELX-02 required on a mg/kg basis. The study drug administration details (including treatment received, date and time of administration) will be listed by subject.

Eloxx Pharmaceuticals

SC injection of ELX-02 will be done in the abdominal region around the umbilicus, by an appropriately qualified, GCP-trained, and experienced member of the study staff, as allowed by local, state, and institutional guidance. A study physician must be present during any ELX-02 administration

3.4 Subject Withdrawal and Replacement

Subjects will be advised that they are free to withdraw from the study at any time. Over the course of the study, the Sponsor and the Investigator or a delegate may withdraw any subject from the study for one of the reasons described below; subject withdrawal will be done in accordance with clinical site SOP:

- Safety reason;
- Non-compliance with protocol requirements;
- Significant protocol deviation;
- Positive alcohol breath test, cotinine test (Group 4 only), drug screen, or pregnancy test;

Hematology, biochemistry, urinalysis, and coagulations results will be reviewed by a PI or a Sub-Investigator prior to dosing; subjects will be withdrawn from the study if it is deemed that the subject's safety may be at risk on the basis of these test results.

For subjects with RI (Groups 1 to 3) and taking medications that are allowed by the Principal Investigator, a positive result to opiate/benzodiazepine/THC screen (drug screen) may derive from the use of the concomitant medications. The subjects will not be automatically withdrawn from the study but will be evaluated on a case-by-case basis by the Principal Investigator. Subjects who withdraw or are withdrawn from the study after dosing will not be replaced. However, in the event that the number of drop-outs exceeds initial expectations, subjects who withdraw or are withdrawn might be replaced at the discretion of the Sponsor. Such replacement resulting in dosing more subjects than planned in this protocol would be documented in a protocol amendment.

Eloxx Pharmaceuticals

Subjects who withdraw or are withdrawn will be asked to remain at the clinic until the PI or a delegate agrees that the subject is fine and can be discharged. As soon as subject withdrawal is confirmed, blood sampling will be stopped. A PK blood draw may be collected at the time of withdrawal if deemed required by the PI. Study exit procedures will be performed at the time of withdrawal from the study or as soon as possible thereafter.

Eloxx Pharmaceuticals

4. Changes from the Protocol

Three changes in planned analyses were done compared to the protocol in this SAP: the PK primary endpoint of AUC_{0-72} was changed to AUC_{0-24} in order to better compare partial AUC across dose groups, the calculation of renal clearance (CL_R) was changed from Ae_{0-72}/AUC_{0-72} to Ae_{0-24}/AUC_{0-24} , and the PK endpoint of T_{max} was changed from a secondary endpoint to a primary endpoint. AUC_{0-72} remains in the analysis as a secondary endpoint. In addition, a clarification was added to indicate that the pharmacokinetic statistical comparisons (i.e.: Mild vs. Control, Moderate vs. Control, and Severe vs. Control) would be done separately.

Eloxx Pharmaceuticals

5. Primary and Secondary Endpoints

 AUC_{0-24} , AUC_{0-t} , AUC_{0-inf} , C_{max} and T_{max} calculated using plasma ELX-02 concentration data and Ae_{0-t} and R_{max} calculated using urine ELX-02 concentration data will be the primary PK endpoints. All other PK parameters calculated for ELX-02 will be regarded as secondary endpoints (refer to Section 10.3).

Safety and tolerability parameters are secondary endpoints (refer to Section 9).

Eloxx Pharmaceuticals

6. Analysis Populations

The analysis of safety and tolerability parameters will be based on the Safety population detailed in Section 6.1. The analysis of PK parameters will be based on the Pharmacokinetic population detailed in Section 6.2.

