Injection site Pruritis	Itching localized to the injection site that is relieved spontaneously or in <48 hours of treatment	Itching beyond the injection site that is not generalized OR itching localized to the injection site requiring ≥48 hours treatment	Generalized itching causing inability to perform usual social and functional activities	NA

The number of subjects (frequency and percentage) will be tabulated for each individual parameter and reaction grading by time point of collection.

10. Pharmacokinetic Analyses

10.1 Handling of the Below the Lower Limit of Quantification (BLQ) and the No Reportable Concentration Values

When handling the below the limit of quantification (BLQ) data the following rules will apply for the derivation of PK parameters:

Eloxx Pharmaceuticals

- Concentration values below the assay's limit of quantification (BLQ) for pre-dose samples will be treated as zero.
- Post-dose BLQ values prior to the first quantifiable concentration will be treated as zero.
- Post-dose BLQ values after the first quantifiable time point that are not followed by measurable concentration will be set to missing.
- The sampling times relative to dosing for pre-dose samples will also be treated as zero.

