10.3 Pharmacokinetic Parameters

10.3.1 Plasma Pharmacokinetic Parameters

For Group 1 to 4, a total of 13 blood samples will be drawn from each subject for quantitation of ELX-02 for pharmacokinetic analyses: 0.250, 0.500, 0.750, 1.00, 2.00, 4.00, 6.00, 12.0, 24.0, 36.0, 48.0, 72.0, and 168 hours post-dose.

Plasma ELX-02 concentrations data will be used to calculate the following parameters by standard non-compartmental methods:

 AUC_{0-24} : Area under the concentration-time curve from time zero to 24 hours post-dose.

Whenever concentration data is missing for the 24-hour post-dose sample for a

subject, calculation of the AUC₀₋₂₄ must not be done.

 AUC_{0-72} : Area under the concentration-time curve from time zero to 72 hours post-dose.

Whenever concentration data is missing for the 72-hour post-dose sample for a

subject, calculation of the AUC₀₋₇₂ must not be done.

AUC_{0-t}: Area under the concentration-time curve from time zero to the last non-zero

concentration, calculated using the linear trapezoidal method.

AUC_{0-inf}: Area under the concentration-time curve from time zero to infinity

(extrapolated), calculated as $AUC_{0-t}+C_t/K_{el}$, where: C_t = the last observed

non-zero concentration.

Eloxx Pharmaceuticals

C_{max}: Maximum observed concentration.

Residual area Residual area, calculated as 100*(1- AUC_{0-t} / AUC_{0-inf}).

 T_{max} : Time of observed C_{max} .

 $T_{\frac{1}{2} \text{ el}}$: Elimination half-life, calculated as $\log(2)/K_{\text{el}}$ using the natural logarithm.

K_{el}: Elimination rate constant. This parameter will be the negative of the

estimated slope of the linear regression of the log-transformed concentration (natural logarithm) versus time profile in the terminal elimination phase. At least 3 concentration points will be used in estimating K_{el} . The time point where log-linear K_{el} calculation begins $(K_{el\ Lower})$, and the actual sampling time of the last quantifiable concentration used to estimate the K_{el} $(K_{el\ Upper})$ will be reported with the correlation coefficient from the linear regression to

calculate Kel.

CL/F: Apparent total body clearance, calculated as Dose/AUC_{0-inf}.

V_d/F: Apparent volume of distribution, calculated as Dose/(K_{el} x AUC_{0-inf}).

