10.4 Statistical Analyses

Renal function assessment will be reported with the method using MDRD4 equation with serum creatinine concentration. GFR estimated with serum creatinine concentrations will be used to classify subjects and this classification will serve for primary analyses.

Individual and mean ($\pm SD$) plasma concentration versus time curves will be presented for both linear and semi-log scales. Descriptive statistics (arithmetic and geometric means, standard deviation [SD], coefficient of variation [CV%], minimum [Min], maximum [Max], and median) of the plasma concentrations versus time will be presented as well for the PK parameters according to renal function groups included in the study (Mild, Moderate, Severe renal impairment, and Control). A graphical description of the relationship between renal function measures and PK will be presented.

For plasma PK parameters, using GLM procedures in SAS, ANOVA will be performed on untransformed T_{max} , K_{el} and $T_{\frac{1}{2}el}$ and on In-transformed AUC_{0-24} , AUC_{0-72} , AUC_{0-t} , AUC_{0-inf} , and C_{max} . Factors incorporated in the model will include Group as a fixed effect. Each statistical comparison (i.e.: Mild vs. Control, Moderate vs. Control, and Severe vs. Control) will be done separately.

Sample code for the procedure in SAS® codes for ANOVA (Mild vs. Control) is specified below:

```
proc glm data=basepk;
where GROUP in ('1','4');
class GROUP;
model VAR = GROUP / ss3;
means GROUP;
lsmeans GROUP / cl alpha=0.1 pdiff;
estimate 'Mild vs. Control' GROUP 1 -1;
run;
```

The ratios of geometric means (Mild/Control, Moderate/Control, Severe/Control) and their associated 90% CI will be calculated according to ANOVA results for AUC_{0-24} , AUC_{0-72} , AUC_{0-t} , AUC_{0-inf} , and C_{max} . Inter-subject Coefficient of variation will be estimated. Two-sided p-values will also be derived as exploratory analyses to provide statistical inferences at the alpha 5% level of significance.

Derived calculations obtained from the ANOVA analyses will be performed as per the following:

• Inter Subject $CV = 100 * SQRT (e^{[MSE]} - 1);$

Eloxx Pharmaceuticals

- Ratio = 100 * e^{DIFFERENCE}, where DIFFERENCE is the point estimate of renal function groups difference (e.g. Mild Control, Mild Control, and Severe Control) on the Intransformed scale; and
- 90% Confidence Limits = 100 * e (DIFFERENCE ± t (dfResidual) * SE (dfResidual) * DIFFERENCE .

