 T_{max} will be analyzed nonparametrically (using the Hodges-Lehmann method) with point estimates and 90% CIs for the median differences of Tmax between groups (Mild-Control, Moderate-Control, Severe-Control).

```
proc npar1way hl alpha=.10 data= basepk; class GROUP; var Tmax; exact hl; ods select WilcoxonScores HodgesLehmann; run;
```

For urine PK parameters, Ae_{0-t} and R_{max} will be analysed in the same manner as plasma PK parameters (AUC_{0-24} , AUC_{0-t} , AUC_{0-inf} , and C_{max}).

In the event that renal impairment has a clinically relevant effect on ELX-02 PK, the relationship between renal function and appropriate PK parameters for ELX-02 (e.g., CL/F, AUC_{0-24} , AUC_{0-72} , AUC_{0-1} , AUC_{0-inf} , and C_{max}) will be determined by a linear or non-linear regression.

Study results including the graphical description and the relationships between renal function and relevant pharmacokinetic parameters will be used to elaborate specific dosing recommendations if deemed clinically relevant.

Additional and exploratory statistical analysis may be performed.

11. Percentages and Decimal Places

If not otherwise specified, the following rules will be applied, with the exception of PK tables and listings described below:

- Percentages will be presented to one decimal point.
- Percentages equal to 0 or 100 will be presented as such without a decimal point.
- Minimum and maximum will be presented with the same precision as the original values and, mean, standard deviation, and median will be presented with one more decimal place than the original values.

All digits will be used for pharmacokinetic and statistical PK calculations. For PK tables and listings, the final reportable results or data will be presented by rounding off to two decimal digits, except for the following situations (this applies to individual data and descriptive statistics):

- K_{el} and correlation (Corr.) data: rounded off to four decimal digits.
- Pharmacokinetic parameters related to time such as T_{max}, K_{el Lower}, and K_{el Upper} must be reported with the same precision as the actual sampling time: rounded off to 3 decimal digits.
- Concentration versus time data, as well as C_{max}: reported as they appear in corresponding dataset.
- Ratios and 90% confidence intervals, and inter-CV (%) will be presented to two decimal places.

Eloxx Pharmaceuticals

12. Data Handling

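### Read together, SAP 10.1, 10.3.1 and 13 leave a typical control with no AUC0-72, and may remove AUC0-24 and CL_R in some controls

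*SAP*

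**What the plan says.** Three rules in the SAP bear on the partial AUCs.

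- SAP 10.1, on deriving PK parameters: "Post-dose BLQ values after the first quantifiable time point that are not followed by measurable concentration will be set to missing".
- SAP 10.3.1 gives AUC0-24 and AUC0-72 matching stop rules. The first begins "Whenever concentration data is missing for the 24-hour post-dose sample" and the second "Whenever concentration data is missing for the 72-hour post-dose sample". In each case the area is then not to be calculated. Protocol 12.1.1 has the same rule for AUC0-72.
- SAP 13 restricts the PK analysis to observed data, makes an exception for BLQ values that refers back to 10.1, and rules out extrapolating or interpolating for missing data.

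The quantities that depend on these rules:

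- SAP 5 lists AUC0-24 among the primary endpoints.
- SAP 10.3.2 defines CL_R as Ae0-24/AUC0-24.
- SAP 10.4 plans the comparisons: "The ratios of geometric means (Mild/Control, Moderate/Control, Severe/Control) and their associated 90% CI will be calculated according to ANOVA results". Its list includes both AUC0-24 and AUC0-72.
- SAP 7 promises interim descriptive statistics for all primary and secondary PK parameters in Groups 1 and 2.

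SAP 4 explains the move from AUC0-72 to AUC0-24 as made "in order to better compare partial AUC across dose groups". SAP 3.3 provides for one dose level: "Each subject will be administered a single SC dose of 1 mg/kg ELX-02".

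**The concern.** A BLQ result is information: the concentration is known to be close to zero. SAP 10.1 turns a trailing BLQ result into a missing value, and SAP 10.3.1 then withholds the area because the value is missing. A subject who has cleared the drug before the end of the window therefore gets no partial AUC, although that area is essentially complete.

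This falls hardest on the control group, which clears the drug fastest and is the denominator of every ratio. Without control values for AUC0-72, its three planned ratios cannot be formed. If the 24 h sample is also BLQ in some controls, a primary endpoint and the reference renal clearance rest on fewer than the planned 6 to 8 subjects. The loss would also be selective: controls with slower elimination would be kept, which tends to raise the control mean and pull the ratios down.

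**Working it through.** **Inputs.** Protocol 5.2.2.2, healthy subjects, 1 mg/kg SC: Cmax 3576 ng/mL, Tmax 1.0 h, half-life 2.14 h, AUC0-12 13,131 ng*h/mL. Protocol 5.1.2: mean half-life 2 to 4 h at 0.3 to 5.0 mg/kg, mean residence time about 3 to 4 h, urinary recovery (Fe) 81.1 to 99.2% after SC dosing and 85.2% after IV. The lower limit of quantification (LLOQ) is not given.

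**Step 1. Check against the protocol's own figure.** A straight rise to Cmax at 1 h, then C(t) = 3576 x 2^(-(t-1)/t½) with t½ = 2.14 h. Linear trapezoid at this study's sampling times gives AUC0-12 = 13,299, which is 1.3% above 13,131. The exact integral gives 12,515 (4.7% below). The inputs describe the control profile adequately.

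**Step 2. Control level at 72 h.**
- t½ 2.14 h: 71/2.14 = 33 half-lives after Cmax, so 3576 x 2^(-33.2) = 3.7e-7 ng/mL.
- t½ 4 h: 71/4 = 17.75 half-lives, so 0.016 ng/mL.
- For assumed LLOQs of 0.1 to 50 ng/mL, a quantifiable 72 h value needs a half-life of at least 4.7 to 11.5 h, outside the stated 2 to 4 h.

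A one-compartment model with first-order absorption (ka 2.27/h, set by Tmax 1 h, scaled to the same Cmax) gives 4.3e-7 ng/mL at t½ 2.14 h.

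**Step 3. Control level at 24 h.** The simple curve gives 3576 x 2^(-23/2.14) = 2.1 ng/mL. The one-compartment model gives:

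| t½ (h) | Model residence time (h) | 24 h level (ng/mL) |
|---|---|---|
| 2.0 | 3.34 | 1.5 |
| 2.14 | 3.53 | 2.4 |
| 2.5 | 4.01 | 6.9 |

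The range stops at 2.5 h because a longer half-life takes the model outside the stated residence time. Over assumed LLOQs of 0.1 to 50 ng/mL, a quantifiable 24 h value needs a half-life of at least 1.5 to 3.7 h, which overlaps the stated range. So the result depends on the assay. With an LLOQ of 2 ng/mL, for instance, the 2.0 h control would be lost and the other two kept.

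**Step 4. Other groups at 72 h.** Same model at t½ 2.14 h, with elimination rate multiplied by 1 - Fe(1 - g), where g is GFR relative to normal (assumed) and Fe runs from 0.811 to 0.992:
- Mild, g = 0.75: about 1e-4 ng/mL.
- Moderate, g = 0.45: 0.01 to 0.13 ng/mL.
- Severe, g = 0.20: 1.4 to 41 ng/mL.

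Under the literal rule AUC0-72 may therefore exist mainly in Severe.

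**Step 5. Effect of using zero.** Linear trapezoid, which the SAP states only for AUC0-t and is assumed here for the partial AUCs. If the 24 h value is replaced by zero, the lost area is C(24) x 12/2:
- t½ 2.0 h: 1.47 x 6 = 8.8 of 15,625, or 0.06%.
- t½ 2.14 h: 2.43 x 6 = 14.6 of 16,349, or 0.09%.
- t½ 2.5 h: 6.85 x 6 = 41.1 of 18,216, or 0.23%.

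Zero for every sample after 12 h changes control AUC0-72 by 0.11 to 0.47%.

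**The case against.** The strongest reply is that the stop rule was meant for samples not drawn or without a result. The AUC0-72 rule comes from Protocol 12.1.1, where there is no BLQ rule and missing most naturally means no result. The title of SAP 10.1 also separates BLQ values from concentrations that are not reportable. This may well be what the authors intended. But SAP 10.1 uses the same word for trailing BLQ values, in rules written for parameter derivation, and nothing in 10.3.1 limits it.

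SAP 13 does make an exception for BLQ values. It only sends the reader back to 10.1, which says missing. SAP 10.3.2 lets the pharmacokineticist leave parameters uncalculated with an explanation. That permits omission and does not lift a prohibition.

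It is fair to say the consequence is limited. AUC0-72 is secondary and CL_R has no planned ratio. AUC0-t and AUC0-inf are primary and remain calculable: SAP 10.3.1 says "At least 3 concentration points will be used in estimating" Kel, and the 4, 6 and 12 h samples supply three in a modelled control. Control AUC0-t is within about 0.1% of AUC0-72 if 24 h is quantifiable, and about 4.5% lower if 12 h is the last quantifiable sample. This objection stands and sets the severity.

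A reader might also infer that the reason given in SAP 4 invalidates the change of endpoint. It does not: read as a slip for renal function groups, the sentence makes sense.

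**Conclusion.** The rules as written prevent AUC0-72 in a typical control, so its planned ratios to Control could not be formed. Mild, and probably Moderate, subjects would also lose it, including in the interim summaries. This holds across the stated half-lives of 2 to 4 h for any LLOQ above about 0.016 ng/mL. Loss of AUC0-24 and CL_R in controls is possible but conditional on the LLOQ; the documents do not support saying that it will happen.

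The result rests on the literal reading of missing and on a monophasic decline, which Protocol 5.1.2 reports at the lowest doses. A slow second phase, reported there from 2.5 mg/kg, would raise late levels. The printed half-life SD equals the mean (2.14 h). If that is real, a control at mean plus 2 SD (6.42 h) would have about 1.7 ng/mL at 72 h, so a few controls might escape.

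A stronger inference would be that AUC0-24 hides total exposure in Severe and that the SAP must name a lead AUC, demote AUC0-24 or set a residual-area limit. The documents do not support it. AUC0-inf and AUC0-t carry ratios and 90% CIs, residual area is reported, p-values are exploratory, no decision rule hangs on one AUC, and the planned regression of "the relationship between renal function and appropriate PK parameters for ELX-02" includes CL/F. At most, the Severe ratios should be read together: with Fe 0.852 the modelled AUC0-24 ratio is about 5% below the AUC0-inf ratio at 29% of normal GFR (2.41 against 2.53) and 9% at 20% (2.87 against 3.14), or 4 to 21% over Fe 0.811 to 0.992.

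Severity: minor.

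**What to change.** - **SAP 10.1 and 10.3.1:** state that the prohibition on AUC0-24 and AUC0-72 applies only when the 24 h or 72 h sample was not drawn or has no reportable result. State that a trailing BLQ value at or before the end of the window enters that partial AUC as zero. Confine the zero to the partial AUCs, so that the existing rule continues to apply to Kel, AUC0-t and AUC0-inf.
- **SAP 13:** add a matching cross-reference.
- **SAP 4:** change *dose groups* to *renal function groups*.

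The cost is SAP wording only, with no new samples or procedures. The price in accuracy is the small understatement of area shown above, and in return AUC0-24, AUC0-72 and CL_R can be computed in every group from the samples already planned.
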